3.4.1 Inclusion Criteria

- 1. Study subjects with definite dystonia (e.g. focal, segmental, multifocal and generalized), as established by a movement disorder specialist.
- 2. Study subjects of any race and either gender, age 18 or more on the date the informed consent form (ICF) is signed and with the capacity to provide voluntary informed consent.
- 3. Study subjects able to read and understand English and the ICF and are willing to comply with all study procedures, treatment and follow-up.

- 4. Study subjects who are taking any central nervous system acting medications (e.g., benzodiazepines, antidepressants, hypnotics), including medications for the treatment of dystonia, will be on a stable regimen for at least 30 days prior to the screening Visit, and will willing to remain on the same dose for the duration of the study.
- 5. Female of child-bearing potential will not be pregnant and will be using an acceptable method of contraception.
- 6. Study subjects with an MMSE >24.

3.4.2 Exclusion Criteria

- 1. Exposure to dopamine blockers prior to the onset of dystonia that could, in the investigator's opinion, have caused dystonia.
- 2. Study subjects with genetically-confirmed dopa-responsive dystonia.
- 3. Study subjects with a diagnosis of Parkinson's or an atypical parkinsonian syndrome.
- 4. Study subjects with a history of bipolar disorder or major depression, or the presence of active depression.
- 5. Study subjects with a history of a suicide attempt or suicidal ideations, as well as the presence of active suicidal ideation as detailed on the C-SSRS administered during Visit 1.
- 6. Study subjects with a history of schizophrenia or schizophrenia spectrum disorders.
- 7. Treatment with tetrabenazine, reserpine, valbenazine, a monoamino oxidase inhibitor, a-methyl-p-tyrosine, strong anticholinergic medications, metoclopramide, antipsychotics, dopamine agonists, levodopa, and/or stimulants within 30 days of screening.
- 8. Treatment with botulinum toxin less than 11 weeks prior to screening (Visit 1); subjects receiving injections sooner than every 12 weeks will be excluded if their next injection is scheduled farther than 6 days from screening.
- 9. Presence of a neurologic condition that could confound dystonia assessments.
- 10. Study subjects with a history of clinically relevant hepatic disease.
- 11. Study subjects with a history of renal insufficiency.
- 12. Any unstable medical illness.
- 13. A corrected QT (Bazett) interval of 450 (458) milliseconds in men or 460 (472) milliseconds in women on 12-lead ECG at screening, or a history of cardiac arrhythmias.
- 14. Study subjects participating in any drug or device clinical investigation concurrently or within 30 days prior to screening for this study.
- 15. Study subjects with a known hypersensitivity or contraindication to the study drug or its components.

3.4.3 Duration of Subject Participation

The duration of study participation will be 13 weeks from screening (Week 1) to the post treatment evaluation (Week 13). Treatment period from drug initiation to final on-treatment Visit will be 12 weeks, or less, as follows:

- Study subjects able to titrate up to 48 mg/day will have 6 weeks of ramp-up and 6 weeks of maintenance.
- Study subjects receiving a strong CYP2D6 inhibitor will only be allowed to titrate AUSTEDO up to a dose of 36 mg/day. They will have will have 4 weeks of ramp-up and 6 weeks of maintenance, for a total of 10 weeks on treatment. The total study duration for these subjects will be 11 weeks, when the final post treatment evaluation is included.
- Study subjects who experience dose-limiting side effects will be maintained on their maximum tolerated dose. Once the maximal dose is established for a study subject, they will complete 6

- continuous weeks on this dose (maintenance period), followed by a 1-week washout. For these study subjects, the 6 weeks of maintenance will start once they reduce the study drug to the maximum well-tolerated dose, independent of the duration of the ramp-up period.
- The duration of the trial for study subjects who experience dose-limiting side effects that arise during the ramp-up period will depend on the dose at which the side effects appear. For these subjects, maintenance will continue to last 6 weeks, and they will also have a 1 week washout.
- Premature, unexpected withdrawal from the trial will shorten study duration for that subject in unpredictable ways; subjects will be asked to undergo an early termination safety Visit, whenever possible.

3.4.4 Estimated Study Duration

As mentioned in the previous section, the AUDYT trial will have a maximal duration of 13 weeks/subject, which includes a 6-week ramp-up period, a 6-week maintenance period, and a 1 week washout. It is expected that 2 subjects will be recruited per month, on average. Thus, recruitment of all study subjects should take 8 months. If the last study subject (recruited during month 8) participates in the study for 13 weeks (the longest possible study duration per subject), this would bring complete study duration from the time of recruitment of the first study subject (Visit 1) to Visit 5 of the last study subject to about 11 months.

- 3.5 Study Visit and Assessment Schedule
- 3.5.1 Schedule for subjects able to increase to and maintain maximum AUSTEDO dose

A diagram summarizing all study visits can be found in the Appendix section (Appendix 1). Details on each of the individual study visits are depicted below.

3.5.1.1 Visit 1: Screening (Week 1)

This will be the first study Visit. During this Visit, subjects will sign the informed consent form, their eligibility for study participation will be confirmed, and study drug will be dispensed. Demographic and baseline characteristics (age at screening, gender, weight, height, BMI, race, ethnicity, medical history, physical examination) will be listed for individual subjects. The activities to be performed during Visit 1 include:

- Informed consent
- Medical history will be obtained
- Medication history will be obtained. All prior medications will be assigned a generic name based on the World Health Organization (WHO) Dictionary.
- Concomitant medications will be reviewed (subjects receiving a strong CYP2D6 inhibitor will be
 instructed to titrate up to 36 mg during the ramp-up period, not to 48 mg, once study drug is
 dispensed). All concomitant medications will be assigned a generic name based on the World
 Health Organization (WHO) Dictionary. When applicable, date of last and next botulinum toxin
 injections will be recorded, as well as the date of the last DBS setting changes.
- Complete physical exam
- Vital signs
- 12-lead ECG
- C-SSRS
- SSS
- MMSE
- First video of the movement disorder examination

- MDS-UPDRS Part III
- Revision of eligibility criteria (inclusion/exclusion criteria will be reviewed)
- Dispense study drug (if eligible for participation)

3.5.1.2 Visit 2: Ramp-up period (Week 2 +/- 2 Days)

Visit 2 will be the first one on study drug. This is a safety Visit, which will happen 5-9 days after study drug initiation. The activities to be performed during Visit 2 include:

- Adverse events will be assessed
- Vital signs
- 12-lead ECG
- C-SSRS
- SSS

Patients will be contacted on a weekly basis via telephone during the ramp-up period to assess study drug tolerability. Dose reductions will be allowed in this period at the discretion of the investigator, but also during the maintenance period. A dose reduction during the ramp-up period will determine the start of the maintenance period, as it will be assumed that the new, lower AUSTEDO dose is the maximum well-tolerated dose of AUSTEDO for that study subject. Similarly, subjects will remain on the new, maximum well-tolerated dose of AUSTEDO for the remainder of the trial once a dose reduction is done during the maintenance period.

3.5.1.3 Visit 3: Maintenance dose starts

This is a safety Visit. The time during which this Visit will happen may vary depending on the duration of the ramp-up period, as follows:

- For subjects able to titrate up to 48 mg/day, Visit 3 will be scheduled during week 7.
- For subjects receiving a strong CYP2D6 inhibitor and, hence, able to titrate only up to 36 mg/day, Visit 3 will happen during week 5.
- For subjects with dose-limiting side effects during the ramp-up period, Visit 3 will be scheduled up to 3 days after the maximal, well-tolerated dose is established (this landmark will determine when the maintenance period has started).

The activities to be performed during Visit 3 include:

- Adverse events will be assessed
- Vital signs
- 12-lead ECG
- C-SSRS
- SSS

3.5.1.4 Visit 4: Maintenance dose ends

Visit 4 will happen during the last week of the maintenance period: during week 12 for subjects on 48 mg/day of AUSTEDO, during week 10 for those subjects receiving a strong CYP2D6 inhibitor, and 6 weeks after the initiation of the maintenance period for subjects who experienced dose-limiting side effects during the ramp-up period. This will be the last visit while on study drug, and at this time

subjects will be instructed on when to stop AUSTEDO. According to the package insert,³ treatment with AUSTEDO can be discontinued without tapering. The activities to be performed during Visit 4 include:

- Adverse events will be assessed
- Vital signs
- 12-lead ECG
- C-SSRS
- SSS
- MMSE
- Second video of the movement disorder examination
- MDS-UPDRS Part III
- Patient Global Impression of Improvement
- 3.5.1.5 Visit 5: Post treatment evaluation

Visit 5 will be scheduled 1 week (or up to 9 days, if necessary) after study drug cessation. This is a safety Visit. The activities to be performed during Visit 5 include:

- Adverse events will be assessed
- Complete physical exam
- Vital signs
- 12-lead ECG
- C-SSRS
- SSS
- Returned bottles will be collected and compliance will be assessed
- 3.5.2 Special situations that could cause changes in Study Visit Schedule
- 3.5.2.1 Shortened Ramp-up Period

There are three scenarios that could shorten the duration of the ramp-up period:

- 1. Study subjects taking a strong CYP2D6 inhibitor: The maximum dose of AUSTEDO allowed for subjects taking a strong CYP2D6 inhibitor will be 36 mg/day. These study subjects will start AUSTEDO at 12 mg/day and increase at weekly intervals in increments of 6 mg per day up to 36 mg/day, if tolerated, as instructed in the package insert.³ For these subjects, the maximum length of the ramp-up period will be 4 weeks.
- 2. Subjects unable to titrate up to the maximum recommended dose: Whether it is 48 mg/day or 36 mg/day, study subjects may experience dose-limiting side effects that do not allow them to titrate up to their individual, maximal recommended dose. Any side effects encountered during the ramp-up period will be recorded and reported as appropriate. Study subjects who encounter these side effects will be instructed to reduce the total daily AUSTEDO dose by 6 mg (1 tablet) every day until a new, maximum well-tolerated dose of AUSTEDO is established. A faster dose reduction will be allowed if deemed necessary by the investigator. Once this new dose is determined, the maintenance period will be considered initiated and subjects will be asked to complete Visit 3 at the study site within 3 days.
- 3. Subjects unable to tolerate 12 mg/day of AUSTEDO: Subjects who are unable to tolerate the starting dose of the study drug will be withdrawn from the trial. Side effects encountered will be recorded and reported as appropriate.
- 3.5.2.2 Early Termination

If at any time during the study a patient requests to withdraw from treatment, or if a decision is made to withdraw the patient from the study, the patient will be requested to return for an Early Termination Visit.

3.5.2.3 Unscheduled Visit

A patient may return for an unscheduled Visit at any time at the Investigator's discretion (for example, when a one week post dose-reduction ECG is required). The procedures conducted at the unscheduled Visit may be limited, depending on the reason for the Visit (for example, for dispensing of new study drug to replace a lost bottle of study drug would only require those specific procedures relevant to the reason for the unscheduled Visit to be done).

3.5.2.4 Dose Adjustment

Adjustments in the dose of AUSTEDO will be allowed throughout the study. If a reduction in the dose of AUSTEDO is required during the ramp-up period due to dose-limiting side effects, study subjects will be instructed to reduce the total daily AUSTEDO dose by 6 mg (1 tablet) every day until a new, maximum well-tolerated dose of AUSTEDO is established. A faster dose reduction will be allowed if deemed necessary by the investigator. Once this new dose is determined, the maintenance period will be considered initiated, and subjects will be instructed to complete Visit 3 and to remain on this dose for 6 weeks. Any side effects encountered will be recorded and reported as appropriate.

Dose-limiting toxicity will be defined in this protocol as the development of any of the following during the titration period: a) new or worsening depression, b) worsening of dystonic symptoms, c) QTc increase of >39 but <60 milliseconds from baseline, or d) any other sign or symptom that, at the PI's discretion, would preclude further safe titration of the study drug.

If a reduction in the dose of AUSTEDO is required during the maintenance period due to dose-limiting side effects, study subjects will be instructed to reduce the total daily AUSTEDO dose by 6 mg (1 tablet) every day until a new, maximum well-tolerated dose of AUSTEDO is established. A faster dose reduction will be allowed if deemed necessary by the investigator. Once this new dose is determined, subjects will be instructed to remain on this dose until the 6 weeks of the maintenance period are completed. A new maintenance period will NOT start every time a dose reduction is performed. Any side effects encountered will be recorded and reported as appropriate.

Increments in the total daily dose of AUSTEDO will not exceed 6 mg/week, as recommended by the package insert.³ Treatment interruptions will be discouraged unless necessary. In these cases, resuming AUSTEDO at the previous maintenance dose without titration will be allowed as long as the subject has been off study drug for 6 days or less. Subjects who require drug cessation for a week or more will be consider withdrawn from the trial, and will be asked to complete an early termination Visit.

3.5.2.5 Subject Withdrawal

Subjects will be advised that they are free to withdraw from the study at any time. Reasons that subjects may be withdrawn from the study include the following:

• Subject discontinued study medication: according to the package insert,³ following treatment interruption of greater than one week, AUSTEDO therapy would need to be re-titrated when resumed, and, thus, subjects who require drug cessation for a week or more will be considered

withdrawn from the trial. For treatment interruption of less than one week, treatment can be resumed at the previous maintenance dose without titration, as per the package insert.³

- Subject consent is withdrawn
- QTc changes: A study subject will be asked to discontinue study drug if at any point during the trial he or she is found on ECG to have developed a QTc> 500 milliseconds or a QTc increase of >60 milliseconds from baseline.
- Sponsor decision, after discussion with the Investigator

If a subject is withdrawn from the study, all efforts will be made to complete the early termination Visit that includes efficacy assessments and safety follow-up. In addition, women of childbearing potential will have a pregnancy test performed at the early termination Visit. All information, including the reason for withdrawal, will be reported. For subjects who are lost to follow-up, three recorded attempts will be made to contact the subject for follow-up information, including reason for discontinuation and follow-up of AEs. Subjects who withdraw from the study will not be replaced.

- 3.6 Study Procedures and Assessments
- 3.6.1 Safety assessments
- 3.6.1.1 Adverse Events

During the study, the Investigator or study site personnel will be responsible for querying and recording adverse events (AEs) and serious adverse events (SAEs). In this study AEs and SAEs will be reported from the time of study drug administration until Visit 5 or death, whichever occurs first.

An adverse event (AE) is any untoward medical occurrence that occurs in conjunction with the use of a medicinal product in humans, whether or not considered to have a causal relationship to the medicinal product. According to the package insert,³ adverse reactions experienced by at least 4% of subjects on AUSTEDO and with a greater incidence than on placebo include somnolence, diarrhea, dry mouth, fatigue, urinary tract infection, insomnia, anxiety, constipation and contusion.

All AEs will be recorded regardless of the severity or relationship to study medication. All AEs that result in permanent discontinuation of the study drug being studied, whether serious or nonserious, will be reported. Figure 1 below shows the form that will capture this data.

	Figure 1		
Date: DD – MMM – YYYY		Study subject number:	

Visit Number (circle one): 1 2 3 4 5 Early termination Visit Other _____

The AUDYT Trial Adverse Event Documentation Form

Description of the AE:		
Diagnosis (if known):		
If AE is an overdose:	Medication error Accider	ntal overdose
	Intentional overdose N/A	
Serious adverse event:	Yes No	
Date/Time of Onset:		
Date/Time of Resolution:		
Relationship to drug:	Probable Possible	_ Not related
Severity:	Mild Moderate S	evere
Outcome:	Recovered	Recovering
	Recovered with sequelae	Not recovered
	Death	
Action taken:	No action taken	Study drug stopped
	Study drug discontinued	Other

3.6.1.2 ECG

AUSTEDO may prolong the QT interval. QT interval prolongation is associated with the development of tachyarrhythmias and Torsades de Pointes. To screen for the development of significant QT

prolongation (defined as a corrected QT –Bazett– interval of 450 (458) milliseconds in men or 460 (472) milliseconds in women), a 12-lead electrocardiogram (ECG) will be performed during all scheduled study Visits, including the early termination Visit, if such a Visit happens. Should there be evidence of QT prolongation, it will remain at the investigator's discretion to either discontinue the study drug, or to reduce the dose to a new, maximum, well-tolerated dose. A follow up ECG will be performed 1 week after the dose reduction (during an unscheduled Visit) to ensure the QT prolongation is no longer significant.

However, a study subject will be asked to discontinue study drug if at any point during the trial he or she is found on ECG to have developed a QTc> 500 milliseconds or a QTc increase of >60 milliseconds from baseline. Study subjects will be asked to come in for an Early Termination Visit within 3 business days of study drug discontinuation.

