2.3 Safety Outcome Assessments

The following assessments will establish the safety and tolerability of AUSTEDO during the AUDYT trial:

- Tolerability will be established by the proportion of study subjects able to titrate up to 48 mg/d (or up to 36 mg/d if receiving a strong CYP2D6 inhibitor) and able to complete the study at this dosage.
- Adverse events will be surveyed during all study Visits and during weekly telephone communications with the study subjects that will happen during the ramp-up period.
- AUSTEDO may prolong the QT interval. QT interval prolongation is associated with the development of tachyarrhythmias and Torsades de Pointes. To screen for the development of significant QT prolongation (defined as a corrected QT –Bazett– interval of 450 (458) milliseconds –or higher– in men or 460 (472) milliseconds –or higher– in women), a 12-lead electrocardiogram (ECG) will be performed during all scheduled study Visits, including the early termination Visit, if such a Visit happens. Should there be evidence of QT prolongation, it will remain at the investigator's discretion whether to discontinue the study drug, or to reduce the dose to a new, maximum, well-tolerated dose. A follow up ECG will be performed 1 week after the dose reduction (during an unscheduled Visit) to ensure the QTc is no longer significantly prolonged.
- A complete physical examination will be performed at the time of the initial and final study Visit, as well as during the early termination Visit, if applicable. Any and all changes in the examination happening during the trial will be recorded, and reported when appropriate.
- Vital Signs (including weight) will be measured and recorded during all scheduled study Visits, including the early termination Visit, if such a Visit happens. Any and all gross abnormalities or significant changes will be reported.
- Suicidal thoughts or actions are a possible side effect of AUSTEDO use. The Columbia Suicide
 Severity Rating Scale (C-SSRS) will be administered during all scheduled study Visits, including
 the early termination Visit, if such a Visit happens. Development of suicidality as determined by
 this instrument at any point during the trial will warrant the immediate discontinuation of the
 study drug, as well as psychiatric care as determined necessary by the investigator. Subjects
 with any signs or suicidality during Visit 1 as detected by the scale will be immediately excluded
 from participating in the trial.

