- Somnolence is a possible side effect of AUSTEDO use. The Stanford Sleepiness Scale (SSS) will be administered during all scheduled study Visits, including the early termination Visit, if such a Visit happens. Should this side effect develop, the investigator will decided whether to continue AUSTEDO at the current dose, to discontinue the study drug, or to reduce the dose to a new, maximum, well-tolerated dose.
- To assess the impact AUSTEDO may have on cognitive function, if any, the Mini Mental State Examination (MMSE) will be administered during Visits 1, 4 and during the early termination Visit, if such a Visit happens. It will remain at the investigator's discretion to either discontinue the study drug, or to reduce the dose to a new, maximum, well-tolerated dose if clinically-

- significant, new-onset cognitive impairment is identified at any point during the course of the trial, even if detected during Visits during which the MMSE is not administered.
- To screen for the development of drug-induced parkinsonism, a possible side effect of AUSTEDO use, the MDS-UPDRS (Part III) will be administered during Visits 1, 4 and during the early termination Visit, if such a Visit happens. It will remain at the investigator's discretion to either discontinue the study drug, or to reduce the dose to a new, maximum, well-tolerated dose if clinically-significant, new-onset drug-induced parkinsonism is identified at any point during the course of the trial, even if detected during Visits during which the MDS-UPDRS (Part III) is not administered.

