Table 6 below shows a list of medications that are known to prolong the QTc. Subjects taking these medication will be allowed to participate in the trial as long as their ECG during visit 1 (and while already on one or more of these drugs at steady state) shows no QTc prolongation. Any evidence of QTc prolongation during subsequent ECGs will require an adjustment in the AUSTEDO dose as detailed elsewhere. The introduction of these medications will not be allowed for the duration of the trial. If it is determined that a subject requires one of these medications during their participation in the trial, AUSTEDO will be stopped and the subject will be considered withdrawn from the trial.

Table 6 Drugs causing QTc prolongation
Moxifloxacin
Quinidine
Procainamide
Amiodarone
Sotalol

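### The on-study QTc limit equals the entry limit, and no repeat ECG is required before a dose reduction that cannot be reversed and fails the primary endpoint

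*Combined protocol and SAP*

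**What the plan says.** Exclusion 13 (3.4.2) bars entry at "A corrected QT (Bazett) interval of 450 (458) milliseconds in men or 460 (472) milliseconds in women on 12-lead ECG at screening". Section 2.3 uses the same pairs of values to define significant prolongation on study, there written as "interval of 450 (458) milliseconds –or higher– in men", with the matching pair for women.

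For what happens when the limit is reached, 3.6.1.2 states: "Should there be evidence of QT prolongation, it will remain at the investigator's discretion to either discontinue the study drug, or to reduce the dose". Section 2.3 gives the same two options. The follow-up ECG is placed after the action, as a check that the limit is no longer exceeded: "A follow up ECG will be performed 1 week after the dose reduction (during an unscheduled Visit) to ensure the QT prolongation". For somnolence, by contrast, 2.3 leaves the investigator to decide "whether to continue AUSTEDO at the current dose, to discontinue the study drug, or to reduce the dose". For subjects on QT-prolonging drugs, 4.8 is firmer: "Any evidence of QTc prolongation during subsequent ECGs will require an adjustment in the AUSTEDO dose as detailed elsewhere".

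Four other rules bear on this:
- **Titration.** The dose-limiting toxicity list (3.1, 3.5.2.4) has its own QTc item: "c) QTc increase of >39 but <60 milliseconds from baseline, or d) any other sign or symptom that", at the investigator's discretion, would make further titration unsafe.
- **Reductions.** A ramp-up reduction starts maintenance at the lower dose. A maintenance reduction holds for the rest of the trial (3.5.1.2, 4.4.2).
- **Unscheduled visits and pauses.** Section 3.5.2.3 allows unscheduled visits at any time, "for example, when a one week post dose-reduction ECG is required". Sections 3.5.2.4 and 3.5.2.5 let a subject who has been off drug for less than a week resume at the previous maintenance dose.
- **Primary endpoint.** Section 3.7.1.1 counts subjects who reach 48 mg/day (36 with a strong CYP2D6 inhibitor) and complete the study at that dose.

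**The concern.** A single QTc reading varies around the subject's usual value. With the same limit at entry and on study, a subject with a usual QTc just under it can cross it by chance. Both listed responses then end that subject's chance of counting as a success. The ECG a week later cannot settle the matter: a normal tracing at a lower dose fits both a noise reading and a true effect that has receded, and nothing lets it restore the dose.

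Section 3.7.1.1 records why subjects fail, but a reading that was never repeated cannot be classified afterwards. The primary endpoint would then mix intolerance with measurement error, in a pilot meant to inform larger trials.

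**Working it through.** **From trigger to endpoint (documents only)**

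1. *Headroom.* The plan does not say which number of each pair applies. If the same number serves both purposes, a man can enter at 449 ms and be acted on at 450 ms: 450 − 449 = 1 ms. If the lower number governs entry and the higher governs action, headroom is 458 − 449 = 9 ms (men) or 472 − 459 = 13 ms (women).
2. *Visit 2* falls 5-9 days after the first dose, at 12 or 18 mg/day. A 6 mg reduction from 18 leaves 12 mg/day, and 12/48 = one quarter of the target, fixed as the maintenance dose. A subject who cannot stay on 12 mg/day is withdrawn (3.5.2.1). Either way the target dose is never reached.
3. *Visit 3* falls at the maximal dose. A reduction there is permanent, so the subject does not complete at that dose.
4. *Weight.* Each failure moves the primary proportion by 1/15 = 6.7 points.

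**How often a reading would reach the limit (illustration)**

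The plan gives no figure for this, so there is none to reproduce. Inputs:
- d = distance of the subject's usual QTc below the limit: 10 or 20 ms (assumption).
- SD of one reading around the usual value: 8, 10 or 15 ms (assumption).
- Drug shift: 0 at Visit 2 (assumption) and 4.5 ms at Visit 3, the mean after a single 24 mg dose in 4.1.3, which is the per-dose amount at 48 mg/day.
- Readings independent between visits (assumption). Visit 4 is left out as the last visit on drug.

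Formulas: p2 = P(Z > d/SD); p3 = P(Z > (d − 4.5)/SD); either visit = 1 − (1 − p2)(1 − p3).

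| d (ms) | SD (ms) | p2 | p3 (Visit 3 alone) | Visit 2 or 3 |
|---|---|---|---|---|
| 10 | 8 | 0.106 | 0.246 | 0.326 |
| 10 | 10 | 0.159 | 0.291 | 0.404 |
| 10 | 15 | 0.252 | 0.357 | 0.519 |
| 20 | 8 | 0.006 | 0.026 | 0.032 |
| 20 | 10 | 0.023 | 0.061 | 0.082 |
| 20 | 15 | 0.091 | 0.151 | 0.228 |

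With no drug effect at either visit, the last column becomes 0.200-0.441 at 10 ms and 0.012-0.174 at 20 ms.

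**With a confirming repeat, d = 10**

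If both readings must reach the limit and are independent, replace each p by p². For SD 8: 1 − (1 − 0.106²)(1 − 0.246²) = 0.071; for SD 15 the result is 0.183. If the two readings correlate at 0.5, the range is 0.148-0.300.

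**What the repeat costs in detection**

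For a subject truly 10 ms above the limit, one reading triggers with probability P(Z > −10/SD) = 0.894 (SD 8) to 0.748 (SD 15). Requiring two independent readings gives 0.894² = 0.800 to 0.748² = 0.559.

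**Is 4.5 ms the right shift?**

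Section 4.1.4 gives a half-life of 9-10 hours. With dosing every 12 hours, accumulation is 1/(1 − 2^(−12/9)) = 1.66 to 1./(1 − 2^(−12/10)) = 1.77. If QTc scales with exposure (assumption), the shift is 4.5 × 1.66 = 7.5 to 4.5 × 1.77 = 8.0 ms. From the upper confidence limit of 6.5 ms it is 10.8 to 11.5 ms, enough to put the on-drug mean of a subject with d = 10 above the limit.

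**The case against.** The strongest reply is that the plan already leaves room to check. An unscheduled visit can be used for a repeat ECG, and a pause of 6 days or less with resumption is allowed. Acting on the first abnormal tracing is also a defensible caution for a QT-prolonging drug not yet studied in dystonia, since 4.1.3 says higher exposures have not been evaluated. Finally, no threshold or test is attached to the primary proportion, so no decision rule changes.

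Much of this stands. A reader might infer that the plan forbids a repeat, or that one borderline reading must produce a failure. The text supports neither. But neither route is required or mentioned in the QT rule, interruptions are discouraged, and resumption at a previous maintenance dose does not clearly cover a subject still titrating at Visit 2.

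A second reply is that the >39 ms item governs titration, so a small rise across the absolute limit at Visit 2 would not call for a reduction. That reading is possible. Sections 2.3 and 3.6.1.2 state no minimum rise and cover all scheduled visits, but the plan does not say how the two rules combine. A reader might call them contradictory; they are better read as separate safety layers. The Visit 2 part of the point is conditional on the absolute limit applying there too.

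**Conclusion.** The point holds as a gap in the QT rule. The action limit equals the entry limit, the listed actions are irreversible for the endpoint, and no confirmation is required first. That link rests on the text alone for Visit 3, and for Visit 2 if the absolute limit applies during titration.

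The size depends on assumptions. With an SD of 8-15 ms and a 4.5 ms shift at Visit 3, the chance of a trigger is 25-36% at Visit 3 alone and 33-52% at Visit 2 or 3 for a subject 10 ms below the limit. At 20 ms below, it is 3-15% and 3-23%.

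Two stronger conclusions are tempting and not supported. The first is that all such triggers would be noise: the shift at 48 mg/day may exceed 4.5 ms, so some would be real. The second is that these percentages describe the trial: they apply only to subjects near the limit, and no baseline QTc distribution is given, so their number among the 15 is unknown. The stop at >500 ms or a rise of >60 ms is not in question. This is a cheap improvement worth making, not a flaw that undermines the study.

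**What to change.** In 2.3 and 3.6.1.2, cross-referenced in 3.5.2.4 and 4.8, add a step for a QTc that first reaches the absolute limit without meeting the >500 ms / >60 ms stop or the >39 ms item:

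- Hold the dose, meaning stay at the current dose with no increase, and repeat the ECG at the same visit or within days.
- If the repeat confirms it, reduce or discontinue as now.
- If not, continue and resume titration.
- The investigator may act on the first reading at any time.

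A >39 ms rise should not become a precondition for acting on the absolute limit. While editing, state which number of each pair applies and how the absolute limit relates to the >39 ms item. Failures due only to the absolute limit could also be listed separately. These are points of detail.

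The cost is wording in four sections, an occasional extra ECG at a visit the plan already permits, and a short delay before a confirmed reduction. Some same-visit sensitivity is lost: 75-89% falls to 56-80% for a subject truly 10 ms above the limit, if two independent readings must both reach it and the investigator does not act on the first.
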